the subarachnoid space can allow CSF to bypass an obstruction, thus obviating the need for a VP shunt. The use of endoscopic third ventriculostomy (ETV) is now becoming more prevalent in the primary treatment of hydrocephalus particularly in cases of obstruction and a consensus of opinion exists regarding their high likelihood of success in these cases¹³. The use of ETV is also gaining popularity in the treatment of shunt malfunction even in cases where there was a communicating hydrocephalus to begin with. There are several papers advocating this (secondary ETV) as a worthwhile alternative to shunt revision. In some cases particularly in older patients ETV has been suggested as a treatment for shunt blockage in patients whose hydrocephalus was originally communicating^{3,5,7,9,20,25}.

In this unit we perform approximately 100 shunt revisions per year. In 2004, we performed 108 shunt revisions. In 47 of those cases (43.5%), a further procedure was needed because of complications with the new shunt. The 1-year survival revised shunts in 2004 was therefore 56.5%. There are series which show higher success rates (70%) with ETV following shunt failure²⁰. These are retrospective.

To date there has been no prospective analysis comparing ETV to shunt revision in patients who present with shunt problems requiring surgery.

Study objective:

The aim of this study is to compare the success rates of ETV and shunt revision in the treatment of shunt malfunction in patients with hydrocephalus, In other words to:

- determine which group of patients are most likely to require further surgery within a one year follow-up period
- To compare immediate complication rates between the two patient groups

Sample population:

All patients presenting to Leeds General Infirmary with shunt obstruction will be considered for the study regardless of the original cause of their hydrocephalus.

Inclusion criteria:

1. Symptoms/signs or radiological evidence of shunt obstruction
2. Ventricular anatomy making an endoscopic procedure feasible as judged by the attending consultant neurosurgeon:
 - a. Lateral and third ventricles adequate size
 - b. Thin third ventricle floor
 - c. Adequate pre-pontine cistern to fenestrate into with an endoscope
3. Age greater than one year

Exclusion criteria

1. Age less than one year (these children are less likely to benefit from ETV^{2,6,14-16,18,23,24})
2. Small ventricles preventing passage of the endoscope

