3. Patients who would not be suitable for a shunt
4. Patients whose condition is such that urgent surgical intervention is needed and time for enrolment is not available
5. Patients who are unable to give consent and there are no available next-of-kin

Sample size:

In order to detect a statistical significant difference ($p < 0.05$) between the two groups we would require 196 patients at. The power calculations were performed by our IT department at Leeds General Infirmary ([name]). This unit performs surgery for approximately 100 patients per year with shunt malfunction and we would therefore calculate that the study will take four years to complete assuming about half of patients will not be suitable for the study or will not wish to take part.

Randomisation process:

We intend to randomise half of our patients to each arm of the study (i.e. 100 will have a shunt revision for their treatment and 100 will have an ETV). This will be done by choosing from a collection of 200 identically sealed envelopes kept in the theatre suite. For obvious reasons the surgeon and patient cannot be blinded to the treatment to which they are randomised.

Consent procedures:

For each patient presenting with shunt malfunction, the surgeon will assess whether they are suitable for the study. Once suitability has been confirmed, consent will be sought in three possible ways:

1. In the case of a patient under 16: The parents of the child will be given an information sheet detailing the reasons for, aims and methods of the study. In the case of a child who has a normal conscious level and is of an age where he/she can understand the study rationale, there is a specific information sheet for the child. A consent form will be signed by the registrar or consultant taking consent and the parents of the child (and the child where appropriate). A separate information for children who can read will be provided.
2. In the case of a consenting adult, with a normal conscious level: Information on the study will be provided as above and written consent obtained by the attending registrar or consultant.
3. In the case of an adult with reduced conscious level or who is mentally unable to comprehend the study: Consent will be sought from the patient's next-of-kin. Where there is no next-of-kin available, the patient will be excluded from the study.

Study procedure:

Before recruitment to the trial:

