Those that are randomised to shunt revision will have part or all of the shunt replaced. Patients randomised to the ETV arm of the study may have the malfunctioning shunt left in situ. Once the patient has had their surgery, they will be kept in hospital until they are deemed well enough for discharge home. There will be a visual assessment prior to discharge.

Follow-up will be arranged for 6 weeks, 6 months and one year for all study patients. At the 6 week and 6 month clinic the patient will have a cranial imaging to assess ventricular size. Those that have had an ETV will have an MRI scan to determine patency of the stoma as well (this is normal practice

following such a procedure). If a shunt revision is performed, a CT or MRI will be performed. Fundoscopy and visual acuity are also assessed in clinic. This is no different from the normal follow-up of a patient who has had treatment of a blocked shunt.

Should a patient make an unscheduled presentation because of symptoms related to their hydrocephalus or surgery and recurrence of the hydrocephalus is suspected they will be investigated in the usual manner in such cases (i.e. clinical and/or radiological confirmation of failure of shunt or ETV if that is the case).

A final proforma will be filled in at the patient's exit from the study. Exit from the study can happen in 3 ways:

- The patient represents with shunt/ETV failure
- The patient is well at one year following surgery with no need for further surgical intervention
- The patient voluntarily withdraws from the study for any reason at all

Duration of the study

Subject to R&D and ethics committee approval, enrolment into the study will commence on January 1st, 2007 and we would expect to enrol the 200th patient by December 31st, 2010. To ensure a minimum of one years-follow-up, data accrual will continue for one year after recruitment of the 200th patient. Overall we would expect this study to last at most 5 years.

Treatment efficacy assessment/endpoints:

In each patient the following endpoints will be assessed:

Primary endpoint:

One-year success rate of the procedure (one-year survival of shunt or ETV)

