- The procedure will be deemed a failure if the patient requires further surgical intervention within a year for treatment of their hydrocephalus. We felt that one-year follow-up was appropriate as most shunt and ETV failures occur in the first year following the procedure^{9,12}. The need for further surgery will be determined clinically or radiologically. In the case of patients who are in the ETV arm of the study, a sagittal MRI demonstrating the third ventricle floor will be sought where possible.

Secondary endpoints:

1. Occurrence of complications from surgery
2. Ventricular size changes
3. Length of inpatient stay
4. Number of re-attendances (excluding scheduled ones at 6 weeks, 3 months and 1 year) with symptoms related to their hydrocephalus/wound or implant.

Safety

Where either treatment would be deemed unsafe, the patient would be excluded from the study.

The risks of surgery are:

1. Death (less than 1% for shunt and ETV)
2. Epilepsy (approximately 5% short term risk in both treatments)
3. Minor vascular injury – Both treatments involve the passage of instruments through the brain to the ventricle. The risk of bleeding from this is about 5%. Most bleeds are sub clinical and don't result in neurological deficit. The risk of a bleed causing a deficit is about 1-2% for both treatments
4. Major vascular injury: This is a risk with ETV where basilar artery injury has occurred - death from it has been reported¹. However, most large series of patients treated with ETV, report no such injuries.
5. Infection: The shunt infection rate in this unit at present is 5%. The rate of CSF infection or ventriculitis is 0-10% in large series^{8,11,21} The rate of infection
6. CSF wound leak: This occurs in up to 5% of newly implanted shunt and is a high risk factor for infection. In the case of ETV it usually means that the ETV will not work and a shunt is needed²¹
7. Overdrainage and slit ventricle syndrome. This is a rare but serious problem in children treated with shunts. It can cause severe headaches and often requires further shunt surgery. It is not a recognised complication of ETV²²
8. Subdural haematomas. This is a complication seen with overdrainage of shunts in adults. It can mean that a patient will require surgery to remove the haematomas and shunt revision. It is also rarely seen with ETVs.

Subject withdrawal

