- ventricle size decreased (still large)
- ventricle size unchanged (normal)
- ventricle size unchanged (still large)
- ventricle size increased
- Other...

MRI

- not done
- ventricle size decreased (normal)
- ventricle size decreased (still large)
- ventricle size unchanged (normal)
- ventricle size unchanged (still large)
- ventricle size increased
- flow through stoma (if ETV)
- Other...

Number of visits post discharge

Complications post-op	Free text
-----------------------	-----------

Status

- Functioning at one year
- Failed before one year
- Dead
- Lost to follow-up

Symptoms in successful patients

- none
- mild
- severe (requiring admissions)

Where failed: Date of failure

- Operation for failure
- shunt
 - ETV again
 - Other...

Cause of failure Free text

Statistical considerations:

The primary endpoints will be compared by a chi-squared test comparing success rates at one year in each group.

The timing of failure in those treatments that do fail will be compared using the Kaplan-Meier survival curves.

Complication rates are expected to be small and we expect no statistical difference in a study this size.

Mean numbers of reattendances and mean reduction in ventricular size will be compared using student's t-test

Data storage

All data will be stored on a PC and in paper form in the neurosurgical department.

Patients will be identified by their hospital numbers and only neurosurgical medical staff will have access to the data

Ethical considerations

There are no specific ethical issues in this study. Both treatments are well-recognised alternatives for managing patients with hydrocephalus

Publication of study findings

We plan to publish the results of this study in Journal of Neurosurgery

Presentations of the data will be made to at academic meetings (e.g. European Society for Pediatric neurosurgery and/or the International Society for Pediatric Neurosurgery)

2. Barlow P: Indications for endoscopic third ventriculostomy: a review of successful and failed cases. **British Journal of Neurosurgery** **11**:456, 1998

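### The Kaplan-Meier comparison is limited to treatments that fail, so the only planned time-to-failure analysis is not a randomised comparison and does not estimate survival of the shunt or ETV

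*Protocol*

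**What the plan says.** Under Treatment efficacy assessment/endpoints, the protocol gives the primary endpoint as "One-year success rate of the procedure (one-year survival of shunt or ETV", closing the bracket there. Failure is defined in the same part: "The procedure will be deemed a failure if the patient requires further surgical intervention within a year for treatment of their hydrocephalus".

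Statistical considerations then gives two analyses that bear on failure. The primary one is: "The primary endpoints will be compared by a chi-squared test comparing success rates at one year in each group". The next sentence is: "The timing of failure in those treatments that do fail will be compared using the Kaplan-Meier survival curves".

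Nothing in the protocol says that patients whose treatment is still working at one year enter these curves as censored observations, and no other time-to-failure analysis is described. Subject withdrawal removes from the final analysis anyone who withdraws before the one-year follow-up. The follow-up proforma has status boxes for functioning, failed, dead and lost to follow-up, and asks for a date of failure where the treatment failed.

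**The concern.** A Kaplan-Meier curve estimates the probability of remaining free of failure among everyone at risk, and patients who have not failed contribute as censored observations. If only failures are entered, nobody is censored and the curve describes something else: how the failures are spread over the year, given that they occurred.

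This has two consequences. First, failure is affected by the treatment, so the failures in one arm are not comparable with those in the other, and randomisation no longer protects the comparison. Second, the number of failures drops out. An arm in which 5% fail and an arm in which 50% fail could give identical curves. Curves labelled as survival would be read as survival of the shunt or ETV, which is how the protocol glosses its primary endpoint, and they would not show it. If the arm with fewer failures tends to fail earlier, the curves would point against the better treatment.

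**Working it through.** **Inputs from the protocol**
- Shunt revision (background section): "The 1-year survival revised shunts in 2004 was therefore 56.5"%, so 43.5% fail.
- ETV (background section): "There are series which show higher success rates (70%) with ETV following shunt failure", so 30% fail. The protocol does not say that this is its planning value; it is used here because it is the only ETV rate given.
- Arm size (Randomisation process): 100 per arm.
- Follow-up: one year.
- Distribution of failure times: none is given, so every timing pattern below is an assumption.

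The plan has no figure of its own to reproduce on this point. The stated sample size of 196 plays no part in it.

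**Patients left out**

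Expected failures: 100 × 0.30 + 100 × 0.435 = 30 + 43.5 = 73.5. Patients not entering the curves: 200 − 73.5 = 126.5, that is 126.5 / 200 = 63%.

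**What the failures-only curve estimates**

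Let S(t) be the probability of being free of failure at t months. With failures only, the curve estimates P(T > t | T ≤ 12) = [S(t) − S(12)] / [1 − S(12)]. At t = 12 this is 0 in both arms for any value of S(12). The quantity of interest, S(12) = 0.70 versus 0.565, cannot be recovered from it.

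**Constant hazards in each arm**

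The hazard ratio is ln(0.70) / ln(0.565) = 0.62 in favour of ETV. The median time among failures is −ln(1 − F/2) / λ, with λ = −ln(1 − F) / 12:
- ETV: −ln(0.85) / [−ln(0.70) / 12] = 5.5 months.
- Shunt: −ln(0.7825) / [−ln(0.565) / 12] = 5.2 months.

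The two medians are almost equal, so nearly all of the difference disappears. In 1000 simulated trials the all-patient log-rank test significantly favoured ETV in 52%. The failures-only test did so in 4%, and it pointed towards shunt in 42%.

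**Other timing patterns**

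These simulations use 100 per arm, 30% versus 43.5% failure, and 1000 to 2000 trials per pattern. Failure times among failures are truncated exponential on 0 to 12 months unless stated. Scales are given as ETV versus shunt, and a positive z means that ETV looks worse.
- 3 versus 3 months (equal timing): failures-only mean z about 0; all-patient mean z −1.95.
- 3 versus 4 months: failures-only significant against ETV in about 16% of trials.
- 2 versus 4 months: failures-only significant against ETV in about 68%; all-patient mean z −1.7.
- 2 months versus uniform over 12 months: failures-only mean z about +5.7, significant against ETV in nearly 100%; all-patient mean z about −1.4.
- 4 versus 2 months (ETV failures later): failures-only mean z −2.4; all-patient mean z −2.2, the same direction.

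The failures-only test follows the timing contrast and ignores the contrast in failure rates.

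**The case against.** The strongest reply is that this sentence governs a supporting analysis. Time to failure is not among the listed endpoints. The primary chi-squared test is not restricted to failures, so the patients left out of the curves are still counted there. Read together, the two sentences ask how many fail and then when the failures happen, and a reader would see both answers. The wording may also be a loose description of an ordinary Kaplan-Meier analysis.

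Most of this stands and limits the point. A reader might infer that the main conclusion of the trial is at risk; the documents do not support that. When failures occur is a fair descriptive question. But the protocol says that timing will be compared between arms, and by survival curves. Nothing in it brings the successes back in, and an analyst following the text literally would produce misleading curves.

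Three other stronger readings should be set aside:
- A reader might infer that the direction is wrong whenever timing differs between arms. It is not: with ETV failures later, both tests agree. Systematic reversal needs the arm with fewer failures to fail earlier.
- A reader might take the near-100% figure as the expected size. It belongs to one extreme assumed pattern. The protocol says only that most failures of both kinds occur in the first year.
- A reader might count the lack of a named test or effect measure as a fault. That is commonly left to a statistical analysis plan, which is not at hand.

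**Conclusion.** The sentence is wrong as written and should be corrected, as a fault in a supporting analysis. It selects on a post-randomisation outcome, leaves out about 63% of patients at the protocol's own rates, and cannot show survival of the shunt or ETV. These statements need no assumption about timing; the 63% rests only on the quoted failure rates and 100 per arm.

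The effect on the comparison depends on failure times that the protocol does not give. With equal timing, a true ETV benefit is lost. With moderately earlier ETV failures, a failures-only test would be significant in the wrong direction in about 16% to 68% of trials, and in nearly all under the extreme pattern. With later ETV failures the direction is right. Whether reversal would occur in this trial cannot be judged from the document.

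**What to change.** Replace the sentence in Statistical considerations with: *Time from surgery to failure will be analysed in all randomised patients by assigned arm using Kaplan-Meier curves, with event-free patients censored at one year; timing among failures will be summarised descriptively only.*

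Two matters must be settled with it:
- Withdrawn or lost patients should be censored at last contact. Subject withdrawal currently excludes from analysis those who withdraw, so the two sections must be reconciled.
- The protocol should state how deaths are handled in this analysis, since the follow-up proforma has a status box for them.

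The cost is small: rewording two places and adding a field to the follow-up proforma. The forms already record the dates of surgery, visit and failure, but show no field labelled for date of death, withdrawal or last contact, so that date would have to be collected.

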The patient who presents with symptoms or signs of shunt malfunction will have a thorough clinical examination, particularly neurological examination. Fundoscopy will be performed in all patients to ascertain the presence or absence of papilloedema. Where possible, a bedside visual field assessment and visual acuity test will be performed with a Snellen chart (competent older children and adults). Imaging will be performed as in all patients with suspected shunt malfunction:

- Shunt series of x-rays
- Cranial CT scan

These are not investigations exclusive to study patients but are performed routinely in such cases.

Where there is doubt as to the cause of the hydrocephalus or the suitability of the patient for ETV and the clinical condition of the patient allows the time a magnetic resonance imaging (MRI) study *may* be performed *prior* to consideration for study entry. This is done in most patients who have not had MR before as most patients presenting to us are assessed for suitability for ETV anyway. If the patient's condition is such that urgent surgery or other intervention is required, this intervention will take precedence over further investigation or entry into the study.

Once a patient is deemed suitable for trial, the patient/carer/parent/next-of-kin will be given information on the study and consent sought. Once written consent has been obtained, the patient is entered into the study. They will be given a study number and a proforma will be filled out. A sealed envelope will be opened to reveal the treatment arm and further consent for surgery will be obtained in the usual manner.

In the cases of those patients who present with shunt infection, they will not be considered eligible for the study until the infection has cleared. Treatment for shunt infection is by removal of the shunt, insertion of an external ventricular drain and administration of intravenous and intrathecal antibiotics for 10 days after the last positive CSF culture. Only at the point where a brand new shunt is considered would the patient be eligible for the study. Shunt infection is not a contraindication to ETV if infection is treated properly beforehand²³.

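### Ventricular size is compared as an unadjusted mean reduction: the test is valid, but it ignores starting size, loses precision, and scores stable normal ventricles the same as stable enlarged ones

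*Protocol*

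**What the plan says.** The endpoint list in the protocol gives secondary endpoint 2 only as "Ventricular size changes". Under Statistical considerations the analysis is fixed: "Mean numbers of reattendances and mean reduction in ventricular size will be compared using student's t-test". No covariate is named.

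On timing, Study procedure says: "At the 6 week and 6 month clinic the patient will have a cranial imaging to assess ventricular size".

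On who enters:
- Inclusion criterion 1 is "Symptoms/signs or radiological evidence of shunt obstruction", so imaging evidence is one route and not a requirement.
- Patients with shunt infection have the shunt removed and an external drain placed, and may enter later: "Only at the point where a brand new shunt is considered would the patient be eligible for the study".
- Two criteria limit the low end of starting size: inclusion 2a, "Lateral and third ventricles adequate size", and exclusion 2, "Small ventricles preventing passage of the endoscope".

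The follow-up form records size by tick-box. One box begins "ventricle size unchanged (normal"; the next is for ventricles that are unchanged but still large. Neither the pre-operative scan block nor the follow-up form, as reproduced, has a field for a measurement.

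**The concern.** How far a ventricle can shrink depends on how large it was. The entry rules allow starting size to differ between patients, both through entry on clinical grounds and through prior drainage. A t-test on raw reduction does not use that information. Two consequences follow.

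- **Precision.** Pre-operative size is likely to predict follow-up size. Leaving it out of the comparison inflates the standard error of the treatment difference.
- **Meaning.** Normal-and-unchanged and enlarged-and-unchanged both give a reduction of zero. The form separates them, but the planned test merges an acceptable result with a poor one.

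For patients drained after infection, the reduction also depends on which scan counts as baseline. Measured from the admission scan, it includes the effect of the drain. Measured from a later scan, it does not.

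**Working it through.** **Inputs.** The protocol gives no standard deviation, correlation, target difference or power for ventricular size, so there is no figure to reproduce. The 98 per arm used below is half of the 196 under Sample size, which was set without reference to this endpoint. All other inputs are assumptions.

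**Formulas.** Let s0 and s1 be the standard deviations before and after, and r the before-after correlation. Per patient:
- change score: s0² + s1² − 2·r·s0·s1
- baseline-adjusted (ANCOVA): s1²·(1 − r²)
- difference between the two: (s0 − r·s1)², which is never negative

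Under these formulas adjustment is therefore never less precise than the change score. With s0 = s1 = 1 the variances are 2(1 − r) and 1 − r², and their ratio is (1 + r)/2.

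**Results with equal spread.** Power is for an assumed true difference of 0.4 SD, 98 per arm, two-sided 5%.

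| r (assumed) | Change score | Adjusted | Ratio | Variance cut | Adjusted n per arm matching 98 unadjusted | Power, unadjusted / adjusted |
|---|---|---|---|---|---|---|
| 0.3 | 1.40 | 0.91 | 0.65 | 35% | 64 | 66% / 84% |
| 0.5 | 1.00 | 0.75 | 0.75 | 25% | 74 | 80% / 90% |
| 0.7 | 0.60 | 0.51 | 0.85 | 15% | 84 | 95% / 98% |
| 0.9 | 0.20 | 0.19 | 0.95 | 5% | 94 | both about 100% |

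The matching n is 98 times the ratio, rounded up; for example 98 × 0.65 = 63.7, so 64.

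**Sensitivity to unequal spread.** If baseline spread were 1.5 times follow-up spread, the variances would be 2.35 v 0.91, 1.75 v 0.75 and 1.15 v 0.51 at r = 0.3, 0.5 and 0.7. The cut is then 61%, 57% and 56%. Nothing in the protocol supports the factor 1.5; it only shows that a wide mix of starting sizes raises the gain. If s0 were as low as r·s1, the gain would be nil.

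**Validity.** In 4,000 simulated trials with 98 per arm and no true difference, 30% of patients (assumed) were given almost no change. The unadjusted t-test rejected in 4.7%, so its error rate holds.

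**The case against.** The strongest reply is that this is an efficiency preference on one secondary endpoint, for which no power is claimed, and that its size rests on assumed correlations. At r = 0.9 the saving is only 5%. That is fair and limits the weight of the point. It does not remove it: the protocol itself fixes the analysis, and any data from which a reduction can be computed already contain the starting size.

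A reader might infer that the trial enrols patients whose ventricles cannot shrink. The protocol does not say so. Inclusion 2a and exclusion 2 both limit small ventricles, and no passage exempts drained patients from them. These are thresholds for endoscopic access and do not require enlargement, so limited room to shrink is possible, but its frequency is unknown. The unchanged-and-normal box does not settle this either, because the form names no comparator scan; unchanged could mean since the previous visit.

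A reader might also infer bias from chance imbalance in starting size. Under randomisation such imbalance is random error, already reflected in the standard error.

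One objection stands in full: the forms hold only categories. As they stand, neither a mean reduction nor an ANCOVA can be computed from them, so adding a covariate is not enough on its own. Choosing the baseline scan could be left to a statistical analysis plan that is not at hand. It is named in the fix because the adjustment depends on it.

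**Conclusion.** The point holds as one of precision and interpretation on a secondary endpoint. The planned t-test is valid but less precise than a baseline-adjusted comparison: the variance is cut by 35% to 5% for an assumed correlation of 0.3 to 0.9 with equal spread. It also gives the same score to stable normal and stable enlarged ventricles. The documents do not support a claim of systematic bias, a claim that enrolled ventricles cannot shrink, or any specific power figure for this endpoint. The power values in the table only illustrate an assumed 0.4 SD difference. The primary endpoint is unaffected.

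**What to change.** Under Statistical considerations, replace the t-test on mean reduction with a comparison of follow-up ventricular size between arms by ANCOVA, with pre-randomisation size as covariate. Define the baseline as the last scan before the envelope is opened, and record its date. Add a numeric ventricular size, read from the existing pre-operative and follow-up scans, and say which follow-up visit supplies the outcome. Analysing follow-up size given starting size separates stable normal from stable enlarged ventricles.

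If only the form's categories are available, compare normal with still large or increased at follow-up by logistic regression, adjusted for enlargement at baseline (yes/no). The variance savings above do not carry over to that model.

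The cost is one measurement field, one date and a revised sentence, plus the time to read the measurements. No extra scans or patients are needed.
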